8.1.2 Acute Exacerbation of Idiopathic Pulmonary Fibrosis

Data on acute exacerbations will be collected. An acute exacerbation of IPF is an acute, clinically significant respiratory deterioration characterized by evidence of new widespread alveolar abnormality [[Collard et al, 2016](#)]. The median survival of patients with IPF who experience an acute exacerbation is approximately 3 to 4 months [[Collard et al, 2016](#)]. Acute exacerbation has been shown to increase the risk of death more profoundly than an absolute decline in FVC percent predicted of \geq 15% [[Paterniti et al, 2017](#); [Ley et al, 2017](#)].

The diagnostic criteria for acute exacerbation of IPF in this study will be as follows [[Collard et al, 2016](#)]:

- Previous or concurrent diagnosis of IPF
- Acute worsening or development of dyspnea typically < 1 month in duration

- Computed tomography (CT) scan results with new bilateral ground-glass opacity and / or consolidation superimposed on a background pattern consistent with a pattern for usual interstitial pneumonia. (If no previous CT scan results are available, the qualifier “new” can be dropped)
- Deterioration not fully explained by cardiac failure or fluid overload

Note: Events that are clinically considered to meet the definition of acute exacerbation of IPF but fail to meet all 4 diagnostic criteria because of missing CT data should be termed “suspected acute exacerbations.”

8.1.3 Pharmacokinetic and Pharmacodynamic Assessments

PK and PD assessments to be conducted during the study are provided in Table 8. Details related to the collection, preparation, and transfer of PK / PD samples will be provided in a Laboratory Manual.

Table 8 Clinical Procedures: Pharmacokinetic and Pharmacodynamic Assessments

Procedure	Description
PK evaluations (central laboratory)	Plasma samples will be collected for assessment of CSL312 concentration.
PD evaluations (central laboratory)	Plasma samples will be collected for assessment of the following parameters: 
 • FXIIa-mediated kallikrein activity • FXII concentration • aPTT

aPTT = activated partial thromboplastin time; FXII = factor XII; FXIIa = activated factor XII; PD = pharmacodynamic; PK= pharmacokinetic.

8.1.4 Biomarker Assessments

The proposed mechanism of action of CSL312 in IPF will be explored using biomarkers of coagulation, inflammation, alveolar epithelial cell damage, tissue modeling, and fibrosis, such as but not limited to, those detailed below.

The following biomarkers will be measured: pF1+2, fibrinogen, D-dimer, aPTT, high-sensitivity C-reactive protein (hs-CRP), and monocytes. Samples will be collected at Screening, before administration of the IV loading dose of investigational product on Day 1, and on Days 8, 36, 64 and 92. hs-CRP will be assessed at all study visits, including Screening, before administration of the IV loading dose investigational product and immediately after the EOI on Day 1.

The following biomarkers will be measured at Screening, before administration of the IV loading dose of investigational product on Day 1, and on Days 8, 36, 64, and 92: FXII (free vs. total), C3a, C5a, IL-8, IL-10, CCL-2, CXCL-1, CCL-18, PAI-1, surfactant protein A (SP-A), surfactant protein D (SP-D), YKL-40, tenascin-C (TN-C), thrombospondin-1 (TSP-1), VEGF, neo-epitope of matrix metalloproteinase-mediated degradation of citrullinated vimentin (VICM), neo-epitope of matrix metalloproteinase-mediated degradation of C-reactive protein (CRPM), pro-Fib, neo-epitope of calprotectin generated by human neutrophil elastase (CPa9-HNE), and collagen synthetic and degradation neo-epitopes (pro-C3/4/6 and C1/3/4/6M).

The following PD parameters and biomarkers will be assessed at all study visits at which PK is being assessed, including before administration of the IV loading dose of investigational product and immediately after the EOI on Day 1: FXIIa-mediated kallikrein activity, FXII concentration, IL-6, and hs-CRP. Additionally, hs-CRP will also be assessed at Screening.

Blood transcriptomics: Blood will be collected for RNA sequencing to investigate changes in gene expression at Screening, before administration of the IV loading dose of investigational product on Day 1, and on Days 8, 36, 64, and 92.

Proteomic analysis: Blood will be collected to characterize the plasma proteome at Screening, before administration of the IV loading dose of investigational product on Day 1, and on Days 8, 36, 64, and 92.

Details related to the collection, preparation, transfer, and storage of biomarker samples will be provided in the laboratory manual. Blood sampling time points for biomarker assessment are indicated in the [Schedule of Assessments](#).

8.1.5 Pulmonary Function Tests

Pulmonary function tests (PFTs) will be performed at the time points indicated in the [Schedule of Assessments](#). The time windows for each type of assessment are detailed in [Section 8.5.1](#).

PFTs, including spirometry and DL_{CO}, will be performed at the study site by the investigator or qualified designee according to the site's SOPs and conducted in accordance with criteria published by the American Thoracic Society (ATS) / ERS [[Graham et al, 2017](#); [Graham et al, 2019](#)]. FVC reference ranges will be those established by the Global Lung Function Initiative [[Cooper et al, 2017](#); [Quanjer et al, 2012](#)].

Before spirometry and measurement of DL_{CO}, long-acting bronchodilators must be washed out for 24 hours and short-acting bronchodilators for 8 hours. Approximately 1 in 10 patients with IPF shows physiological evidence of reversible airflow limitation, and bronchodilator use in these patients may improve the assessment of disease progression based on FVC change over time. Bronchodilator use does not appear to meaningfully affect the precision of FVC as an endpoint in clinical studies [[Assayag et al, 2015](#)].

The decline in FVC is an accepted measure of disease course and reliably predicts mortality in patients with IPF [[Paterniti et al, 2017](#); [Zappala et al, 2010](#); [Flaherty et al, 2003](#); [Collard et al, 2003](#); [Quinn et al, 2019](#)]. A decline in FVC of $\geq 10\%$ has been correlated with worse survival time in patients with IPF [[Paterniti et al, 2017](#); [Zappala et al, 2010](#); [Flaherty et al, 2003](#); [Collard et al, 2003](#)] and recent evidence-based guidelines state that an absolute decrease in FVC of $\geq 10\%$ over time is an acceptable method for assessing disease progression and estimate risk of future mortality in patients with IPF [[Raghu et al, 2011](#)]. Some studies suggest that an FVC decline $\geq 5\%$ may also be clinically significant [[Zappala et al, 2010](#); [du Bois et al, 2011](#)]. Using a relative (rather than an absolute) change in FVC has been shown to maximize the chance of identifying a $\geq 10\%$ decline without sacrificing prognostic accuracy [[Richeldi et al, 2012](#)]. The change in FVC has been used as the primary endpoint in several randomized controlled studies in subjects with IPF [[Raghu et al, 2008](#); [Raghu et al, 2012](#)] including those for the approved drugs nintedanib and pirfenidone [[Richeldi et al, 2014](#); [Noble et al, 2011](#)].

This study is a 14-week, placebo-controlled study. In both the INPULSIS studies and the INBUILD study with nintedanib in patients with IPF and progressive fibrosing interstitial lung diseases, respectively, a clear difference in the mean change in FVC from Baseline between the nintedanib groups and the placebo group is apparent at 12 weeks [Richeldi et al, 2014 (INPULSIS 1 and INPULSIS 2); Flaherty et al, 2019 (INBUILD)]. Similarly, a treatment effect is evident at Week 13 in the ASCEND study with pirfenidone in patients with IPF [King et al, 2014]. This study will determine if the FVC is altered by treatment with CSL312 over a 14-week period in patients with IPF.

As a safety parameter, single-breath DL_{CO} will be assessed at Screening, before administration of investigational product on Day 1 (Baseline), and at Week 14 (EOT / EW Visit). DL_{CO} will be assessed at the study site by the investigator or a qualified designee according to the site's SOPs, and conducted in accordance with criteria published by ATS / ERS [Graham et al, 2017]. The DL_{CO} reference ranges used will be those established by the Global Lung Function Initiative [Stanojevic et al, 2017]. DL_{CO} will be corrected for hemoglobin retrospectively using a blood sample collected on the same day as the DL_{CO} measurement, if available.

8.2 Blood Samples

During the study, blood will be taken from each subject for laboratory safety assessments, PK, and relevant PD and exploratory biomarkers. Repeat or unscheduled blood samples may be taken for safety reasons or for technical issues with the samples.

Information on the volume of blood to be collected for each visit will be available in the informed consent form (ICF).

Refer to the Laboratory Manual for details about the volume, collection, storage, handling and processing of blood samples.

8.3 Retention of Samples

Refer to the Laboratory Manual for further details about the storage and destruction of retention samples.

8.3.1 Retention Samples for Exploratory Biomarkers

Residual blood samples from the exploratory biomarker samples obtained during the Treatment and Observation Period at the time points indicated in the [Schedule of Assessments](#), including the EOT Visit (Day 92) will be stored for potential testing of IPF biomarker and assay development and will be destroyed within 15 years or according to regional or local regulatory requirements after the completion of the study.

8.4 Concomitant Therapies

All drugs and procedures currently being administered to a subject at the time of signing informed consent, and which continue to be taken in addition to investigational product during study participation, are regarded as concomitant therapies.

8.5 Visit Schedule

8.5.1 Assessment Time Windows

The timing and frequency of the study visits, as well as time windows, are described in the [Schedule of Assessments](#).

8.5.2 Screening Period

All subjects (or the subject's authorized representative) must provide written informed consent before any study-specific assessments or procedures are performed. Written informed consent is not required for assessments or procedures performed according to standard of care (eg, for diagnosis or treatment); results from such assessments may be used in the determination of study eligibility.

A screening examination should be performed within 28 days before the intended date of dosing (Day 1). If a potential subject was not enrolled into the study within 28 days of the first Screening Visit, the potential subject may attend a second Screening Visit (for a maximum of 2 Screening Visits per subject). In the event that a potential subject is screened twice, all screening assessments must be repeated at the second Screening Visit, with the exception the 12-lead ECG, which may be repeated separately from other assessments, as necessary. The Sponsor's medical monitor may also grant permission for tests to be repeated separately from other tests as necessary.

If the subject is not eligible for the study (ie, the subject is a screen failure), all eligibility criteria that are not met will be recorded in the eCRF.

8.5.3 Treatment and Observation Period

On Day 1 (Baseline), subjects who complete all screening assessments and who fulfill the eligibility criteria (ie, eligible subjects) will be enrolled into the study and randomized to investigational product on Day 1 (Baseline).

Subjects will continue participation in the study for the 14-week Treatment and Observation Period. Subjects will be asked to return to the site for safety, PK, and efficacy assessments at the time points indicated in the [Schedule of Assessments](#). Subjects will be contacted by telephone on Day 154 (± 5 days) for safety follow-up.

An IV loading dose of investigational product (CSL312 or placebo) will be administered on Day 1. Subjects subsequently will receive 3 doses of investigational product administered SC. The first SC dose will be administered 7 days after the IV loading dose and the second and third SC doses will be administered every 4 weeks (Q4W; on Day 36 and Day 64).

8.5.4 Unscheduled Study Visit

Unscheduled study visits are possible and all assessments performed should be documented in the unscheduled visit page in the eCRF.

Additional data given to CSL may include any medical information from hospital records required by the study but not outlined in the study protocol. This information may be required to help scientific understanding of study data and might be collected even after the completion of the study

8.5.5 End-of-Treatment Visit

The scheduled end of study participation for an individual subject occurs with completion of the EOT Visit on Day 92 ± 2 days, after which no further study-related procedures will be performed.

8.5.6 Follow-up Telephone Call

On Day 154 (\pm 5 days), the investigator (or delegate) will contact the subject by telephone to collect data on AEs (including acute exacerbation of IPF symptoms) and concomitant medications. The Follow-up Telephone Call should be scheduled to occur 90 days after the last administration of investigational product.

8.5.7 Withdrawal

If a subject is withdrawn from the study before the Week 14 Visit (EOT Visit), the investigator should make every effort to perform the assessments during the subjects last study visit or, if possible, encourage the subject to return to the study site for EOT assessments.

9 Adverse Events

9.1 Definitions

9.1.1 Adverse Event

As per the ICH Topic E2A (Clinical Safety Data Management: Definitions and Standards for Expedited Reporting), an AE is any untoward medical occurrence in a patient or clinical investigation subject administered a pharmaceutical product and which does not necessarily have a causal relationship with this treatment. An AE can, therefore, be any unfavorable and unintended sign (including an abnormal, clinically significant laboratory finding), symptom, or disease temporally associated with the use of a medicinal (investigational) product, whether or not it is considered related to the medicinal (investigational) product.

The period of observation for AEs extends from the time the subject gives informed consent until the end of study (see [Section 9.4](#) for further details).

AEs may include:

- Exacerbation (ie, an increase in the frequency or severity) of a pre-existing condition. Illness present before study entry should be recorded in the medical history section of the eCRF and only be reported as an AE if there is an increase in the frequency or severity of the condition during the study.
- A clinical event occurring after consent but before investigational product administration.
- Intercurrent illnesses with an onset after administration of investigational product.

AEs do not include:

- Events identified at Screening that meet exclusion criteria
- Medical or surgical procedures (the condition that leads to the procedure is the AE)
- Situations where an untoward medical occurrence has not taken place. For example:
 - Planned hospitalizations due to pre-existing conditions that have not worsened.
 - Hospitalizations that occur for procedures not due to an AE (eg, cosmetic surgery).
 - Hospitalizations for a diagnostic procedure where the hospital stay is less than 24 hours in duration or for normal management procedures (eg, chemotherapy).
 - Overdose of investigational product or any concomitant therapy that does not result in any adverse signs or symptoms.

For laboratory safety parameters, any instances of absolute values being outside the reference range, or changes at any visit after study start that are considered by the investigator to be clinically significant, must be recorded in the eCRF as AEs. In addition, at the investigator's discretion, any changes or trends over time in laboratory parameters can be recorded in the eCRF as AEs if such changes or trends are considered clinically relevant, even if the absolute values are within the reference range.

Laboratory findings do not need to be reported as AEs in the following cases:

- Increases in aPTT will not be classified as AEs because CSL312 is expected to cause an increase in these parameters.
- Laboratory parameters already beyond the reference range at screening, unless a further increase / decrease can be considered an exacerbation of a pre-existing condition.
- Abnormal laboratory parameters caused by mechanical or physical influences on the blood sample (eg, in vitro hemolysis) and flagged as such by the laboratory in the laboratory report.
- Abnormal parameters that are obviously biologically implausible (eg, values that are incompatible with life or outside the measuring range).
- An abnormal laboratory value that cannot be confirmed after repeat analysis, preferably in the same laboratory (ie, the previous result could be marked as not valid and should not necessarily be reported as an AE).

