2.1.2 Primary Endpoints

Endpoints	Summary Measure
Subjects experiencing treatment-emergent adverse events (TEAEs) including: 
 • SAEs • AESIs • CSL312-induced ADAs • Clinically significant abnormalities in laboratory assessments that are reported as AEs 	Number and proportion of subjects experiencing the specified safety events after treatment with investigational product (CSL312 or placebo)

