Results of laboratory tests (hematology, coagulation, biochemistry, and urinalysis) completed at the central laboratory should be signed and dated and retained at the study site as source data. The investigator should make an evaluation of the available safety-assessment results with regard to clinically relevant abnormalities. Refer to [Section 9](#) for information on how AEs based on laboratory tests should be assessed and reported.

Laboratory Parameters

Details related to the collection, preparation, storage, and transfer of blood and urine samples for laboratory assessments will be provided in the Laboratory Manual.

Refer to [Section 9.1.1](#) for assessment of abnormal laboratory values. Tests resulting in abnormal laboratory values during the study period that have been classified by the investigator as clinically significant should be followed up after receiving the laboratory report, and may include an unscheduled repeat safety sampling at the discretion of the investigator.

Vital Signs

Blood pressure and heart rate will be measured with the subject in a supine or seated position after resting for 5 (\pm 3) minutes. Body temperature will be measured either sublingually or tympanically, and the method of measurement should be consistent throughout the study for a given subject.

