4.1 Objectives and Endpoints

The primary objective of this study is to investigate the safety of CSL312 in subjects with IPF.

The secondary objectives of the study are:

1. To characterize the systemic PK of CSL312 in patients with IPF.
2. To investigate the PD activity of CSL312 in patients with IPF.

The exploratory objectives of the study are:

1. To investigate the potential effect of CSL312 on FXII-related pathways in patients with IPF.
2. To investigate the effect of CSL312 on lung function in patients with IPF.

Table 1 Study Objectives and Endpoints

Objectives	Endpoints and /or Estimand	Summary Measure(s)
Primary	Subjects experiencing treatment-emergent adverse events (TEAEs) including: 
 • Serious adverse events (SAEs) • Adverse events of special interest (AESIs [bleeding events, thromboembolic events (TEE), severe hypersensitivity]) • CSL312-induced antidrug antibodies (ADAs) • Clinically significant abnormalities in laboratory assessments that are reported as adverse events (AEs) 	Number and proportion of subjects experiencing the specified safety events after treatment with IP (CSL312 or placebo)
Secondary		
1	Plasma PK parameters after SC administration of CSL312 at each SC dosing interval: 
 • Trough plasma concentration (C_{trough}) • Maximum plasma concentration (C_{max}) (last SC dosing interval only) • Time to reach maximum plasma concentration (T_{max}) (last SC dosing interval only) • Area under the plasma concentration-time curve after the first dose interval (AUC_{0-tau}) (last SC dosing interval only) 	
 • Mean (SD) and geometric mean (geometric percent coefficient of variation [geometric %CV]) for all PK parameters except for T_{max} • Median (minimum, maximum) for T_{max}

Objectives	Endpoints and /or Estimand	Summary Measure(s)
1	Plasma PK parameters after the IV dose of CSL312: 
 • C_{max} • T_{max} • C_{trough} 	
 • Mean (SD) and geometric mean (geometric %CV) for all PK parameters except for T_{max} • Median (minimum, maximum) for T_{max}
2	Effect of treatment with CSL312 on activated coagulation factor XII (FXIIa) mediated kallikrein activity	
 • Mean (SD) change from Baseline in FXIIa-mediated kallikrein activity by treatment • Mean percentage of Baseline in FXIIa-mediated kallikrein activity by treatment
Exploratory		

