A laboratory value that is outside the reference range is either high abnormal (value above the upper limit of the normal [ULN] reference range) or low abnormal (value below the lower limit of the normal [LLN] reference range). An abnormal laboratory value is not necessarily of potential clinical interest. For each of the hematology and serum biochemistry lab tests, shift tables will be constructed to compare the individual subject baseline value with respect to the normal range to their Day 92 (or last observed value prior to Day 92 in case of dropouts or missing assessment at Day 92) value with respect to the normal range.

The denominator in percentage calculation at a scheduled visit will be based on the number of subjects with a non missing value at that particular visit. The definition of the baseline assessment is given in [Section 8.2.3](#).

A by-subject listing of all laboratory values including flag for values out of normal range will be provided. By-subject listing will include in general all visits (scheduled and unscheduled).

Immunogenicity:

The number and percentage of subjects with a positive immunogenicity test (presence of binding antibodies to CSL312) at any time and separate for Day 36 and Day 92 during treatment will be summarized by treatment group for the analysis population (Safety Analysis Set) as described in [Section 11](#).

A by-subject listing for immunogenicity will be provided.

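### Protocol 9.1.1 wrongly treats an off-scale laboratory result as an example of an implausible one, so a real extreme value may be left out of a primary-endpoint component

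*Protocol*

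**What the plan says.** Protocol Section 9.1.1 sets a general duty: laboratory values outside the reference range, or changes after study start, that are "considered by the investigator to be clinically significant, must be recorded in the eCRF as AEs". It then lists exceptions under the lead-in "Laboratory findings do not need to be reported as AEs in the following cases". Two of the five matter here:

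- Fourth exception: "Abnormal parameters that are obviously biologically implausible (eg, values that are incompatible with life or outside the measuring range".
- Fifth exception: "An abnormal laboratory value that cannot be confirmed after repeat analysis, preferably in the same laboratory". A gloss adds that the earlier result could be marked as not valid and would not necessarily be reported.

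The third exception, for results disturbed by mechanical or physical effects on the sample, applies only where the laboratory has flagged the problem. The fourth and fifth carry no such condition.

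The primary endpoint in Protocol Section 2.1.2 includes "Clinically significant abnormalities in laboratory assessments that are reported as AEs". SAP Section 4.1 repeats it as "Clinically significant abnormalities in laboratory assessments that are reported as adverse events (AEs".

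**The concern.** A measuring range is the span over which an assay returns a number. A result beyond it says only that the true value lies below the lower limit or above the upper one. That is a censored observation. It may be an artefact, or it may be the most extreme true value in the trial. Being off-scale does not by itself make a result implausible.

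By offering it as an example of the obviously implausible, Section 9.1.1 allows a site to leave such a value unreported without any statement from the laboratory that it is invalid. A milder out-of-range value that the investigator judges clinically significant must be recorded. Because this component of the endpoint is defined through AE reporting, a finding that is not reported is not counted. For real values the example can only lower the count.

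**Working it through.** **1. The plan's own figure.** Protocol Section 10.1 and SAP Section 4.4 give 70 evaluable subjects, 12% dropout and 80 enrolled (40 per arm). 70 / (1 − 0.12) = 79.5, rounded up to 80; conversely 80 × 0.88 = 70.4. The figure reproduces and this point does not disturb it.

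**2. The right denominator.** The Safety Analysis Set (Protocol 10.2.2, SAP 6.2) is everyone who received any part of a dose. The planned denominator is therefore about 40 per arm, not the 35 evaluable at Week 14. One uncounted subject moves an arm's proportion by 1/40 = 2.5 percentage points, and only if that subject has no other qualifying laboratory AE.

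**3. How the plan treats off-scale results elsewhere.** SAP Section 12.1 lists drug concentrations below the quantification limit as below that limit and tabulates their percentage. SAP Section 13.1 tabulates the same percentage for kallikrein activity. Some post-dose values below the limit are set to missing in the concentration summaries, but none is called implausible. SAP Section 11.3 has no rule for off-scale safety results in numerical summaries.

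**4. Size, under assumptions only.** Let p be the share of subjects with a clinically significant laboratory abnormality and f the share of those left unreported because of the exemption. The documents give neither. Assume 40 per arm, independent subjects, the same p and f in both arms, and no second qualifying laboratory AE.

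- Expected missed per arm = 40 × p × f
- Chance of missing at least one of 80 = 1 − (1 − p f)^80

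| p | f | Missed per arm | Chance of at least one missed in 80 |
|---|---|---|---|
| 5% | 5% | 0.1 | 18% |
| 10% | 10% | 0.4 | 55% |
| 20% | 10% | 0.8 | 80% |
| 10% | 50% | 2.0 | 98% |
| 20% | 50% | 4.0 | over 99% |

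At f = 0 nothing is lost. The range runs from no effect to a material one, and the documents do not say where in it the trial would fall.

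**5. Effect on the comparison.** With equal f, the observed risk difference is the true difference times (1 − f), and the risk ratio is unchanged. For assumed true risks of 20% and 10%, the 10-point difference becomes 9.5 points at f = 5%, 7.5 at f = 25% and 5 at f = 50%; the ratio stays at 2. If f differed between arms, the ratio would change as well.

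**6. What would still show the value.** SAP Section 11.3 requires a by-subject listing of all laboratory values with an out-of-range flag, and summaries of measured values by scheduled visit. It classifies results against normal limits ("A laboratory value that is outside the reference range is either high abnormal"). The shift tables, however, compare baseline only with Day 92 or the last value before it, so they would miss a mid-study extreme. Unscheduled values appear only in listings (SAP 8.2.5). For the data monitoring committee, laboratory data are listed while AEs are tabulated (SAP 4.5.1).

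**The case against.** The strongest reply is that the exemption is permissive and governed by its opening test. Findings need not be reported, but nothing forbids it. The test is obvious biological implausibility, and the parenthesis only illustrates it. A sensible investigator would not call a plausible D-dimer above the assay limit implausible, and the duty to record clinically significant values remains. This stands against any claim that values will be lost. It does not rescue the example, which tells the site that off-scale results belong in the implausible class.

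A lower count is also not always an undercount, since removing spurious results is the purpose of the rule. That is right, and it is why the example should depend on documentation from the laboratory.

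Four stronger readings are tempting, and the documents do not support them.

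- *The component is undercounted.* No rate is given and none can be derived. Only a possibility is shown.
- *Real transient values are exempted by the unconfirmed-repeat case.* This needs Section 9.1.1 to be joined to Section 8.1.1, where follow-up "may include an unscheduled repeat safety sampling at the discretion of the investigator". That passage concerns values already judged clinically significant and does not mention the exemption. The gloss in 9.1.1 concerns analytical validity, and on re-assay of the same specimen a true transient value would be expected to be confirmed. What remains is an undefined term: specimen, time window and decision-maker are not stated. Protocol Section 4.2, on screening repeats, does separate laboratory error from a reversible condition.
- *The data disappear from the laboratory tables.* No text removes results marked not valid, and all values are listed.
- *Bleeding or thromboembolic events could be hidden.* They are events of special interest in their own right (Protocol 9.1.3), form a separate primary component and have expedited reporting (9.6.2).

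**Conclusion.** The point holds as a wording error with a limited consequence. The measuring-range example is wrong, and it allows real, extreme, clinically significant values to be omitted from a component of the primary endpoint. The possible undercount is of unknown size: 2.5 percentage points per affected subject at 40 per arm, if that subject has no other qualifying laboratory AE. This rests on some off-scale results being real and on some sites using the example as written; the documents establish neither frequency.

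The values stay in the flagged listings. The endpoint is descriptive with no primary hypothesis (SAP 4.1.1), so no sample size, power or alpha is affected. The undefined repeat analysis in the fifth exception is a secondary clarification only.

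**What to change.** In Protocol Section 9.1.1, delete the reference to the measuring range from the fourth exception, or limit it to results the laboratory documents as invalid. Add that a result reported as below or above the assay limit is assessed by the investigator for clinical significance like any other value.

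As a secondary clarification, state in the fifth exception that repeat analysis means re-assay of the same specimen or a laboratory-documented error, so that a normal later sample does not by itself invalidate the first result.

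The cost is about two sentences in the protocol and matching text in the eCRF completion guidance. No new tests are needed. The downside is a few more laboratory AEs to assess and record.
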